### **Background:**

#### *Endothelial Disease and Cardiovascular Risk*

Cardiovascular disease is the leading cause of death for both men and women in the United States. Millions of people world-wide suffer from cardiovascular disease, with 84 million people suffering in the United States alone. It is estimated that one American dies of cardiovascular disease every 40 seconds.

Compromised endothelial function has been implicated with the development and progression of cardiovascular disease. The arterial endothelium is recognized as a smart barrier and key regulator of blood flow in micro- and macrovascular beds. Healthy, distensible arteries allow smoothing of blood pressure variations and ensure blood flow in one direction.

Endothelial dysfunction presents as arterial stiffness, inflammation and lack of vascular relaxation. As arteries stiffen and lose elasticity, pulsatility is dampened causing wider blood pressure fluctuations within the micro- and macrovasculature. These fluctuations and the resultant low diastolic blood pressure place vital organs such as the heart, brain and kidneys at risk. There is a reduction in coronary artery perfusion and increased risks of stroke, renal impairment and hypertrophic heart disease. Furthermore, the effects of shear stress on these stiff vessels promote vascular remodeling and thickening. Endothelial thickening coincides with a decreased production of endogenous vasodilatory mediators, such as nitric oxide, further creating non-distensible arteries without a propensity for vascular dilation. Ultimately this thickening and lack of elasticity fail to properly regulate blood flow and further vital, end-organ damage results.

#### *Heat Therapy and Endothelial Function*

In humans, previous work has demonstrated that heat exposure can improve arterial endothelial function. In sedentary adults, heat therapy via water immersion had widespread beneficial effects on vascular dilatation and a reduction in arterial stiffness. After eight weeks (4-5 times/week) of heat therapy, participants had several markers of improved vascular reactivity including increased flow-mediated dilatation (FMD), improved arterial compliance, reduced aortic pulse wave velocity, decreased carotid intima media thickness and decreased blood pressure.

Other studies utilized infrared, dry sauna therapy daily for eight weeks in patients with cardiovascular risk. In patients with at least one coronary risk factor, flow-mediated dilatation was improved by 5.3%. This improvement translates into substantial improvements in vascular health as improvements of just 2% have been correlated with a 15% reduction in cardiovascular risk. A follow up study showed that in patients with congestive heart failure, heat therapy not only improved flow-mediated dilatation but also decreased plasma brain natriuretic peptide (BNP) levels indicating less congestive heart failure burden.

#### *Mechanism of Endothelial Improvement: Heat Shock Proteins*

A major mechanism thought to be involved in the improvements in vascular tone with heat therapy are the expression of heat shock proteins (HSP). Heat shock proteins are cytoprotective molecular chaperones that accelerate cellular repair and block cell death. Heat shock proteins are also thought to be beneficial to arterial integrity in that there is association of anti-inflammatory and anti-oxidative effects with HSP response. In addition, in bovine coronary endothelial cells, one particular HSP, Hsp90, has been shown to be associated with the critical step by which endothelial nitric oxide is produced. Nitric oxide is an important

and potent arterial vasodilator. Another HSP, Hsp72, is thought to be the HSP most important for thermotolerance by decreasing gut-associated endotoxin translocation and by reducing the body's inflammatory response. Transgenic mice overexpressing Hsp72 display a 2-fold increase in running capacity relative to wildtype mice and exhibit a 50% increase in mitochondria. Increased expression of Hsp72 could therefore contribute to an increase in aerobic capacity following chronic heat therapy.

### Study Aim:

#### *Translation of Endothelial Modifications using Heat Therapy into Cardiovascular Fitness Improvement*

In this study, we will assess if the reported improvements in endothelial function translate into improved cardiovascular function. Since heat therapy has been shown to illicit several molecular markers of benefit for endothelial function including enhancement of FMD and other markers of arterial distensibility, there is a potential direct benefit for cardiovascular health and fitness. As of today, these benefits remain theoretical.

Improvements in cardiovascular function are measured by increased exercise tolerance with various strategies of fitness testing. Historically, the gold standard of fitness testing relies on measurements of maximal oxygen consumption ( $VO_{2max}$ ). There are numerous methods to obtaining  $VO_{2max}$ , however some methods are invasive, require significant equipment and/or require intense exercise by the participant. The methods chosen for this study are validated, utilize two different mechanisms of  $VO_{2max}$  measurements in order to enhance reliability, are noninvasive and require minimal exercise in which the participant can rest when needed to ensure safety.

Oxygen consumption testing ( $VO_2$ ) will be measured with a treadmill exercise respirometry study. This test measures  $VO_2$  indirectly by measuring energy expenditure. This method is known as indirect calorimetry and is the gold standard for measuring energy expenditure. Study participants will complete the treadmill exercise respirometry on the day of their first hot tub immersion, prior to the hot tub session. This exercise will also be performed on within 24 to 48 hours of the final hot tub experience.

We will also measure and record various hemodynamic data points prior to, during and after hot tub sessions utilizing the ClearSight® (Edwards Lifesciences, Irvine, CA) monitor. This noninvasive monitor incorporates a disposable, single use finger-tip blood pressure cuff which accurately calculates blood pressure, stroke volume, stroke volume variation, cardiac index and systemic vascular resistance. It is important to measure these data points in order to investigate the effect of heat therapy on the cardiovascular system since all of these data points are functions of arterial distensibility. Alterations to these hemodynamic variables is directly reflective of cardiovascular tone. This information will further the understanding of the relationship of heat therapy and endothelial tone in a real-time and an *in vivo* setting.

ClearSight finger probe and monitor read out.

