### *Study Cohort and Safety*

Twenty adults, age 50 or older, will be included in the study. Demographic data required for pertinent calculations will be obtained from each participant including height, weight, age and gender. Exclusion criteria includes current major cardiovascular disease known to the patient including recent myocardial infarction, stroke, angina pectoris, high grade coronary vasculopathy or atherosclerosis, severe valvular disease, current cardiac dysrhythmia that requires treatment (i.e. atrial fibrillation, atrial flutter, frequent ventricular premature beats and/or implantation of permanent pacemaker/defibrillator). Patients with a history of coronary artery bypass grafting, valvular surgeries and coronary interventions will be assessed as to current exercise tolerance and symptomology. Other exclusion criteria include current treatment with steroids or immunosuppressive agents, current malignancy, serious liver disease, end-stage renal disease or judgement by a medical provider that water or heat therapy poses an undue burden or risk upon the individual. All females of child bearing age will consent to pregnancy testing and will be excluded if pregnant. Should a participant become hemodynamically or cognitively impaired during any portion of the study activities, 911 will be called for evaluation and possible transport to the emergency department at TUKH. Volunteers can choose to recuse themselves from any or all of the study activities at any time.

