#### *Cardiovascular performance: Oxygen consumption measurements*

Study participants will complete the treadmill exercise respirometry at their first study visit. This exercise will also be performed on within 24 to 48 hours of the final hot tub experience. This waiting period will obviate the transient enhancements of cardiac output and systemic vascular resistance due to water immersion that may alter  $VO_{2max}$  assessments. These effects are normalized shortly after removal from the water and heat sources, thus should be normalized and not have impact on  $VO_{2max}$  by this time. This waiting period also allows for muscle rest prior to the exercise step test. Importantly, waiting until the next day to perform the laboratory and exercise testing also ensures that the changes seen are not acute benefits of heat therapy, but are chronic.

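### The protocol claims two VO2max methods for reliability and refers to a step test, but schedules one oxygen measure, and its minimal-exercise wording does not describe a test that measures VO2max directly

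*Protocol*

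**What the plan says.** The Study Aim calls VO2max the historical gold standard of fitness testing. It notes that some ways of obtaining it are invasive, or "require significant equipment and/or require intense exercise by the participant". Against these it sets the study's own choice: "The methods chosen for this study are validated, utilize two different mechanisms of" VO2max measurement, with reliability as the stated purpose. The same sentence says the methods "require minimal exercise in which the participant can rest when needed to ensure safety".

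The next paragraph describes one method, treadmill exercise respirometry. It calls the measured quantity VO2 and says the method "is known as indirect calorimetry and is the gold standard for measuring energy expenditure".

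The section on cardiovascular performance (oxygen consumption measurements) places the same treadmill test at the first visit and again 24 to 48 hours after the last immersion. It explains the wait partly by the need to protect the VO2max assessment. It then adds: "This waiting period also allows for muscle rest prior to the exercise step test".

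The Measurements section lists what is collected at T1 and T2: ClearSight hemodynamics with heart rate, VO2 by treadmill respirometry, and blood tests. The Objectives section treats improved oxygen consumption and VO2max as the same outcome and says that this translation has not yet been studied.

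**The concern.** There are two linked problems.

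First, the protocol credits itself with a reliability safeguard, agreement between two independent methods, that its own schedule does not contain. A reader of the Study Aim would give the result more weight than the design earns.

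Second, the description of the test does not fit the name of the outcome. A directly measured VO2max needs effort at or near the participant's limit. Light exercise with rest on request gives an oxygen uptake that depends on how hard the participant chose to work. The study compares one group before and after therapy, with no control group and no second method. If the test is run as described, a difference in effort between T1 and T2 would look like a change in fitness. The study's central question would then not be soundly answered.

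**Working it through.** No power, alpha or effect-size figure is involved, and the protocol gives no number to reproduce. The check sets the sections side by side.

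**1. Methods claimed and scheduled**

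| Section | VO2max or oxygen methods |
|---|---|
| Study Aim, general statement | 2 mechanisms claimed |
| Study Aim, description | 1 described (treadmill respirometry) |
| Oxygen consumption measurements | 1 timed (treadmill respirometry); a step test mentioned once, not described |
| Measurements | 1 listed (treadmill VO2); 0 step tests |

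2 claimed − 1 scheduled = 1 method missing.

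**2. Could ClearSight be the second mechanism?** No. By the Study Aim's own account the monitor "accurately calculates blood pressure, stroke volume, stroke volume variation, cardiac index and systemic vascular resistance". None of these is an oxygen-consumption measure, and the blood tests do not supply one either.

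**3. Where the missing method may have gone.** References 26 to 29 cover heart rate variability, a heart-rate-based VO2max fitness test and a step-test web page. The body text cites none of them: its citations pass from 22–25 in the oxygen consumption section to 30 in Objectives. This suggests that a second method was removed and its wording left behind. That is an inference, and the contradiction stands whether or not it is right.

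**4. Name of the outcome and description of the test.** The body text mentions VO2max 7 times: 3 in the Study Aim, 2 in the oxygen consumption section and 2 in Objectives. Of these, 3 are general background or concern a future heart-failure study, which leaves 7 − 3 = 4 about this trial's own methods or outcome. The Measurements list has 0 and says VO2. The intended construct is therefore named, but the list of data to be collected uses a different term. The only text on how hard participants will work is the minimal-exercise sentence in the Study Aim, and that does not describe a direct measurement of a maximum. No section gives a maximal-effort criterion, a fixed load or an estimation rule that would reconcile the two.

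**5. Extent.** Twenty participants at two time points give up to 20 × 2 = 40 treadmill tests to which the mismatch applies. The size of any effort-related change between T1 and T2 cannot be calculated, because the protocol gives no VO2 values, variability or treadmill loads.

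**The case against.** The strongest reply is that this is editorial residue. The operative text agrees in three places (the treadmill paragraph of the Study Aim, the oxygen consumption section and the Measurements list) on one treadmill test before the first immersion and one after the last. Deleting a few stray phrases would change no procedure. Effort criteria and load steps may also sit in a laboratory procedure: the Risks section cites a separate procedure for rapid cooling, although none is cited for the treadmill. A Methods figure is not available either.

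Much of this stands. The schedule itself is clear, and missing test-conduct detail alone would not be a finding. But no separate procedure or figure makes the two-mechanism statement true, and the minimal-exercise wording is positive text that conflicts with the named outcome.

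A reader might infer more than the protocol supports:

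- **That the endpoint is unnamed.** It is named: the oxygen consumption and Objectives sections both say VO2max. The fault is that the listed measure and the test description do not match that name.
- **That an estimated VO2max is intended, because of "Demographic data required for pertinent calculations will be obtained from each participant including height, weight, age and gender".** Cardiac index is also scaled to body size, so the sentence has an ordinary use and says nothing reliable about the endpoint.
- **That exercise-test safety is neglected.** This is a separate question. General cover exists: for example, patients with previous cardiac procedures "will be assessed as to current exercise tolerance and symptomology", and staff monitor continually for adverse events.
- **That the result will be biased by effort.** This follows only if the minimal-exercise wording governs how the test is run, and that wording may be left over.

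**Conclusion.** The point holds in two parts of different strength.

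The textual contradiction is certain. Two VO2max mechanisms are claimed, one oxygen measure is scheduled, and the step test is mentioned once and scheduled nowhere. The reliability claim is wrong for the study as planned.

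The mismatch between the name VO2max and the described test is also on the page, but its consequence is conditional. If participants exercise lightly and rest at will, a change from T1 to T2 could reflect effort rather than fitness and could not be read as a change in VO2max. If the wording is a remnant and the test is in fact maximal, the harm is limited to a misdescription. The protocol does not say which applies, and no size can be put on the effect.

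This deserves correction even in a 20-person pilot, because the Objectives section intends the findings to frame a later heart-failure study.

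**What to change.** 1. Delete the two-mechanism reliability claim from the Study Aim and the step-test reference from the oxygen consumption section. Alternatively, if a second test is really intended, add it to the Measurements list at T1 and T2.
2. Use one endpoint term in the Study Aim, the oxygen consumption section, Measurements and Objectives, matched to the test actually run:
   - **Either** peak VO2 from a symptom-limited graded treadmill test, with the minimal-exercise and rest wording removed, and respiratory exchange ratio and heart rate during the test recorded at T1 and T2 so that effort can be compared.
   - **Or** a submaximal or estimated VO2 at identical loads at T1 and T2, reported as such, with no claim to have measured VO2max.

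The cost is a short amendment to four sections. The first option adds a few recorded variables from the same treadmill session; Measurements already lists heart rate, but with the ClearSight monitor rather than as a treadmill reading. The second option fits the present minimal-exercise wording better, but leaves the study with a more modest claim. Keeping a second test instead would add that test at both time points.

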## Methods:

[figure not shown]
All experimental procedures will be approved through TUKH institutional review board prior to advertisement for volunteers. Participants will volunteer in response to advertisements placed in public areas in The University of Kansas Health Systems. All subjects will provide oral and written informed consent prior to participation. Monetary compensation of \$100 will be offered upon completion of the study. The hot tub used to provide immersion is located in the Clinical and Translational Science Unit (CTSU), Fairway, KS.

### *Study Cohort and Safety*

Twenty adults, age 50 or older, will be included in the study. Demographic data required for pertinent calculations will be obtained from each participant including height, weight, age and gender. Exclusion criteria includes current major cardiovascular disease known to the patient including recent myocardial infarction, stroke, angina pectoris, high grade coronary vasculopathy or atherosclerosis, severe valvular disease, current cardiac dysrhythmia that requires treatment (i.e. atrial fibrillation, atrial flutter, frequent ventricular premature beats and/or implantation of permanent pacemaker/defibrillator). Patients with a history of coronary artery bypass grafting, valvular surgeries and coronary interventions will be assessed as to current exercise tolerance and symptomology. Other exclusion criteria include current treatment with steroids or immunosuppressive agents, current malignancy, serious liver disease, end-stage renal disease or judgement by a medical provider that water or heat therapy poses an undue burden or risk upon the individual. All females of child bearing age will consent to pregnancy testing and will be excluded if pregnant. Should a participant become hemodynamically or cognitively impaired during any portion of the study activities, 911 will be called for evaluation and possible transport to the emergency department at TUKH. Volunteers can choose to recuse themselves from any or all of the study activities at any time.

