### *Hot Water Immersion Therapy*

Previous reports have demonstrated that benefits from heat therapy require 5-14 days to become apparent. Thus, participants in the present study will undergo 8-10 shoulder-high hot water immersions of 40.5°C for 45 minutes/session during a 14-16-day period. Either 1) a rectal probe with sterile disposable sheaths or 2) a sterile rectal thermistor probe will be used to monitor the subject's temperature ( $T_{re}$ ). These probes are inserted approximately 2.54 cm past the anal sphincter. The subject will be removed from the hot tub if  $T_{re}$  is 38.5°C or higher. Participants will be asked to sit on a bench of the hot tub with until  $T_{re}$  is < 38.0°C at which time they may return to the hot tub. Participants are able to drink water *ad libitum* while in the hot tub.  $T_{re}$  will be monitored for 10 additional minutes following emersion from the hot tub or until  $T_{re}$  < 38.0°C.

Hot tub located in the CRC at KUMC.

Subjects will have dry weights measured prior to and after hot water therapy. If body weight loss following therapy is > 1%, the participant will be asked to drink additional fluids to make up the difference. Heart rate will be monitored continuously during heat therapy. If heart rate is altered > 50% from baseline, the participant will

be assessed for neurologic and hemodynamic changes. If there are changes concerning these assessments, the subject will be removed from the hot tub, temperature monitored, and a medical provider notified. Blood pressure will be obtained prior to and after hot water therapy. Participants with pre-therapy systolic blood pressure < 75mmHg or > 180mmHg and/or diastolic blood pressure < 40mmHg or > 90mmHg, will not be allowed to participate in hot water therapy. If post-hot tub blood pressure varies by > 20% lower or > 30% higher than baseline values, the subject will be monitored until return to < 20% deviation from baseline. If blood pressure values do not return to baseline after 10 minutes, discussion with a medical provider will take place prior to discharge from CTSU. If at any time, should a participant become hemodynamically or cognitively impaired during any portion of the study activities, 911 will be called for evaluation and possible transport to the emergency department at TUKH.

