#### **Risks:**

##### *Whole-Body Heat Therapy:*

There are some risks associated with heat exposure, including: fatigue, light-headedness, muscle cramps, dehydration, and neurological detriments (i.e. heat stroke). However, these symptoms do not typically occur until core temperature rises above 40°C. Core temperature (rectal thermistor) will be continuously monitored and recorded. Subjects will be removed from the hot bath immediately if either core temperature reaches 39.5°C or the subjects experience any symptoms of heat-related illness. All symptoms subside upon lowering core temperature. Ice packs will be on hand if rapid cooling is necessary (see Rapid Cooling SOP). Heart rate will also be continuously monitored and recorded throughout heating. If HR increases > 60 beats/min above resting or increases > 20 beat/min with a 5 min time period, subjects will be moved to a seated position if they were previously fully submerged, or removed from the hot tub if they were already sitting up. Additionally, heat exposure may have detrimental effect on a developing fetus in females. Thus, subjects who are pregnant or trying to conceive will be excluded from the study. This will be confirmed with a pregnancy test.

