##### *Rectal temperature probes:*

The use of rectal probes to measure core temperature carries minimal risk. The primary risk is of damage to the lining of the rectum; however, this risk is very slight as we use a flexible thermistor that is designed for this

purpose. We will exclude any subjects who have had recent rectal, anal, vaginal, or prostate surgery. In addition, we will exclude any subjects who have a personal history of heart disease, as the use of a rectal thermometer can cause a vagal reaction, increasing the potential for arrhythmias and fainting. There is also the risk of infection, either by the subject not washing their hands properly or exposure by others to a poorly cleaned probe. We will use clean, sterile disposable probes to minimize this risk. The risk of infection is similar to that of having a bowel movement, and is considered minimal (similar to daily experience). There is also the risk of embarrassment. The approach is typically well tolerated by subjects, and the investigative team is professional in regard to their treatment of the subjects.

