### **Assessment of Subject Safety and Development of a Data and Safety Monitoring Plan:**

Nursing and study staff will continually monitor participants for adverse events. Any adverse event will be immediately reported to the PI and study coordinator per KUMC Human Subject Committee reporting policies. This procedure will be scheduled when a CTSU safety monitor is available. The Principal investigator will assess safety data after every 5 subjects are enrolled. If a trend of adverse events related to heat-related illness occurs, the study will pause or stop until the safety issue is assessed and addressed by the study team.

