### *Objectives*

The main objective of this pilot study is to understand the relationship between the molecular mechanisms of cardiovascular improvements demonstrated in previous studies due to heat therapy to functional cardiovascular improvements in humans. The translation of enhanced endothelial arterial distensibility into improved oxygen consumption, or  $VO_{2max}$ , has yet to be studied. If indeed, the benefits of heat therapy do translate into better cardiovascular health, the implications of this would be far reaching for millions of people who suffer from cardiovascular disease throughout the world.

The current pilot study will measure cardiovascular function following hot water therapy in patients without significant cardiovascular disease. However, the findings of this study will hopefully set the framework for hot water therapy in patients with NYHA Class II -III heart failure in a future study. The benefits in these patients may not only be in  $VO_{2max}$  and biomarker measurements of cardiac function improvements, but also in activities of daily living. This would have a very meaningful impact on society due to the large and ever-increasing number of patients with heart failure. Currently the National Institute of Health recognizes heart failure as major public health problem with a prevalence over 5.8 million Americans and 23 million people worldwide. Heart failure has been singled out as an emerging epidemic. Furthermore, the need for research is increasing as each year more than 550,000 new cases of heart failure are diagnosed in the United States.

Importantly, the amount of healthcare expenditure on heart failure is staggering. More than one million hospitalizations for heart failure occur yearly. Additionally, commonly prescribed medications to treat the symptoms associated with this disease are expensive and many are not covered by major health insurance companies.

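### The eligibility section gives people with prior bypass, valve surgery or coronary intervention a route to enrolment, while the rectal-probe section excludes anyone with a history of heart disease

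*Protocol*

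**What the plan says.** Two sections of the protocol deal with volunteers who have had heart disease.

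- **Study Cohort and Safety** opens its cardiac criteria with "Exclusion criteria includes current major cardiovascular disease known to the patient including recent myocardial infarction" and goes on to stroke, angina, high-grade coronary disease, severe valve disease and rhythm disorders under treatment. Earlier surgery and intervention get a sentence of their own: "Patients with a history of coronary artery bypass grafting, valvular surgeries and coronary interventions will be assessed as to current exercise tolerance and symptomology". No result of that assessment is named as leading to exclusion. The section also allows exclusion on "judgement by a medical provider that water or heat therapy poses an undue burden or risk upon the individual".
- **Rectal temperature probes**, under Risks, says "we will exclude any subjects who have a personal history of heart disease, as the use of a rectal thermometer can cause a vagal" reaction, with arrhythmia and fainting as the feared result. It sets no limit of time or severity and offers no assessment route. The same section describes the probe risk as minimal.

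Two further sections show who is exposed to the probe. Hot Water Immersion Therapy says "Either 1) a rectal probe with sterile disposable sheaths or 2) a sterile rectal thermistor probe will be used to monitor" temperature, and Whole-Body Heat Therapy says "Core temperature (rectal thermistor) will be continuously monitored and recorded".

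**The concern.** On any ordinary reading, someone who has had bypass grafting, valve surgery or a coronary intervention has a history of heart disease. The eligibility section gives that person an assessment that might be passed. The probe section gives a flat refusal. Neither section refers to the other, and the stricter rule stands in a risk paragraph rather than among the eligibility criteria.

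What is at stake is a safety exclusion for which the protocol gives its own reason. A coordinator who screens from the eligibility section could admit a well-functioning volunteer with a past bypass. That volunteer would then have a rectal probe at each of 8 to 10 sessions of 45 minutes in shoulder-high water at 40.5°C, which is the exposure the probe section meant to spare such people. A coordinator who refuses the same volunteer unassessed follows the probe section but departs from the eligibility section.

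**Working it through.** No arithmetic applies, because the point depends on no sample size, power or event figure. The check sets the sections side by side and looks for anything that reconciles them.

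**1. Does the probe exclusion reach everyone?** Yes. Both devices allowed in Hot Water Immersion Therapy are rectal, and Whole-Body Heat Therapy also names a rectal thermistor. No other way of measuring core temperature is offered, so the exclusion cannot be confined to a subgroup.

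**2. Does the assessment sentence leave people eligible?** By implication, yes. It stands apart from the listed exclusions and looks at present tolerance and symptoms. If everyone with this history were excluded anyway, the assessment would decide nothing.

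**3. The same volunteer under each section**

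| Volunteer aged 50 or older | Study Cohort and Safety | Rectal temperature probes | Conflict? |
|---|---|---|---|
| Past bypass, good tolerance, no symptoms | Assessed; may be enrolled | Excluded | Yes |
| Past valve surgery, same state | Assessed; may be enrolled | Excluded | Yes |
| Past coronary intervention, same state | Assessed; may be enrolled | Excluded | Yes |
| Old infarction, no surgery or intervention | Not mentioned | Excluded | No: the probe section adds an exclusion |
| Recent infarction | Excluded | Excluded | No |
| No heart disease, past or present | Not excluded on this ground | Not excluded on this ground | No |

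The opposed answers are confined to the first three rows.

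**4. Does anything say which rule prevails?** No section ranks the two rules. The provider-judgement exclusion is case by case and, as worded, is about water or heat therapy. It could be read to cover the probe, since the probe is described under Hot Water Immersion Therapy, but it would still not decide between an assessment and a blanket bar.

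**5. Do the other safeguards settle it?** They lessen the risk once a person is in the study, but they do not decide eligibility:
- continuous heart-rate monitoring, and blood-pressure limits before each immersion;
- the emergency call if a participant becomes impaired during any study activity, which includes probe use;
- adverse event reporting, and a safety review after every 5 enrolled subjects;
- termination of the procedure for any adverse event of CTCAE grade 3 or higher, whatever its cause (Definition of Adverse Experiences).

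The rule for pausing the whole study is narrower: "If a trend of adverse events related to heat-related illness occurs, the study will pause or stop". A vagal reaction to the probe is not a heat-related illness as that sentence is worded.

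**The case against.** The strongest reply is that exclusions add up. The eligibility list is introduced as an open one, and other exclusions also appear only under Risks, namely trying to conceive and recent rectal, anal, vaginal or prostate surgery. The assessment sentence never says in terms that anyone will be enrolled, whereas the probe exclusion is mandatory and covers every subject. A volunteer must clear every exclusion, so the stricter rule already binds.

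This reading is plausible and lowers the seriousness of the point. It does not remove the defect, because it leaves the assessment sentence with nothing to decide. A reader of the eligibility section alone would not learn that the outcome is already fixed.

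The other side is also right that the route to harm is indirect. It needs staff to screen from one section only, and no screening form is among the documents.

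Two stronger readings are tempting, and the text supports neither:

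- A reader might infer that the sections also contradict each other on an old infarction, since only a recent one is listed. The eligibility section is silent there and its list is open, so the probe section simply adds that exclusion. Some such volunteers would in any case be caught as having high-grade coronary disease or by provider judgement.
- A reader might take the Objectives as a third, rival rule: "The current pilot study will measure cardiovascular function following hot water therapy in patients without significant cardiovascular disease". That sentence describes the population in general terms. It is not an eligibility criterion.

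**Conclusion.** The point holds for prior bypass grafting, valve surgery and coronary intervention. For these volunteers the eligibility section implies possible enrolment and the probe section forbids it. This rests on two readings: that an assessment is meant to let some people through, and that such procedures count as a history of heart disease. Both are ordinary readings, but neither is spelled out.

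Its size cannot be given as a number. The protocol states neither how common past heart disease is among likely volunteers nor how often the probe provokes a vagal reaction. One such enrolment would be 1 of 20 participants (1/20 = 5%), but that only restates the cohort size and measures neither frequency nor harm. A reader might infer a demonstrated danger to participants or a distorted oxygen consumption result. The document supports neither: it calls the probe risk minimal, and nothing in it links the conflict to bias in the outcome.

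This should be fixed, because it is an inconsistency in a safety exclusion and is cheap to remove. It is not a flaw that undermines the study, given that the stricter rule can be read as already binding and other safeguards are in place.

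**What to change.** In Study Cohort and Safety:

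1. Delete the sentence that sends people with prior bypass grafting, valve surgery or coronary intervention to an assessment.
2. State there that volunteers with a history of heart disease are excluded, including prior bypass grafting, valve surgery, coronary intervention or myocardial infarction at any time. Naming the conditions matters because the protocol does not define heart disease.
3. Align the narrower cardiac criteria in the same paragraph with that rule: infarction only if recent, valve disease only if severe, rhythm disorder only if it needs treatment. Left as they are, they would sit beside a blanket exclusion and create a new mismatch.
4. Use the same wording in Rectal temperature probes and on the screening form.

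Narrowing the probe exclusion instead would also remove the conflict. It would give up a protection for which the protocol states a reason, so the sponsor would need to justify that choice.

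The cost is a wording change to the protocol and the screening form, and a somewhat smaller recruitment pool. The documents do not allow the loss to be estimated.
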